6.5 CONCOMITANT THERAPY

Supportive care (eg, antiemetics, analgesics, blood transfusions, hematopoietic growth factor support) may be used at the investigator's discretion and in accordance with institutional procedures. Localized radiotherapy used for palliative purposes may be considered after discussion with the Medical Monitor. Low dose aspirin and anticoagulation with low-molecular weight heparin or direct Factor X inhibitors and LMWH are allowed. Prophylactic LMWH is also allowed for high risk patients with hypercoagulability. Contraceptives are also allowed throughout the study as described in Appendix 4 ([Section 10.4](#)).

Antacids are permitted but should not be consumed within 3 to 4 hours before or after SAR442720 administration.

Any medication or vaccine (including over-the-counter or prescription medicines, vitamins, and/or herbal supplements) that the participant is receiving at the time of enrollment or receives during the study must be recorded along with:

- Reason for use
- Dates of administration including start and end dates
- Dosage information including dose and frequency
- Route of administration

The Medical Monitor should be contacted if there are any questions regarding concomitant or prior therapy.

Participants must abstain from taking prescription or nonprescription drugs (including vitamins and dietary or herbal supplements) within 7 days (or 14 days if the drug is a potential enzyme inducer) or 5 half-lives (whichever is longer) before the start of study intervention until completion of the follow-up visit, unless, in the opinion of the Investigator and Sponsor, the medication will not interfere with the study.

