E 22. Medication and supplements that may interfere or potentiate with SAR442720 and/or adagrasib metabolism or toxicity PRIOR or DURING study intervention are excluded:

- Strong CYP3A4 inducers or inhibitors (within 7 days prior)
- Strong P-glycoprotein (P-gp) inhibitors (eg, cyclosporine, tacrolimus; within 7 days prior)
- Strong Breast Cancer Resistance Protein (BCRP) inhibitors (eg, eltrombopag; within 7 days prior) (applies to Part-3 only)
- Proton pump inhibitors (within 3 days prior) or H2-receptor antagonists (within 1 day prior) during the dose escalation portion of the study
- Medications known to prolong QTc interval
- Acetylsalicylic acid (low dose aspirin, anticoagulation with low-molecular weight heparin or direct Factor X inhibitors and LMWH are allowed. Prophylactic LMWH is also allowed for high risk patients with hypercoagulability).

Diagnostic assessments

E 23. Inadequate organ and bone marrow function at the Screening visit:

- Absolute neutrophil count (ANC) $<1000 \mu\text{L} (1 \times 10^9/\text{L})$.
- Platelets $<100 \times 10^3 \mu\text{L}$ (after at least 3 days without platelet transfusion).
- Hemoglobin $<9 \text{ g/dL}$ or $<5.6 \text{ mmol/L}$ (without transfusions within 2 weeks of initiation of IMP).
- Total bilirubin $>2 \times \text{ULN}$.
- AST and/or ALT $>3 \times \text{ULN}$ (or $>5 \times \text{ULN}$ for participants with liver metastases).
- Blood creatinine $>1.5 \times \text{ULN}$ or creatinine clearance of $<50 \text{ mL/min}$ (using Cockcroft Gault formula or 24-hour urine collection)
- Prothrombin time (PT)/international normalized ratio (INR) and activated partial thromboplastin time or partial thromboplastin time (aPTT/PTT) $>1.3 \times \text{ULN}$ or outside the therapeutic range of the local laboratory if receiving therapeutic anticoagulation that would affect the PT/INR.

Other exclusions

E 24. Individuals accommodated in an institution because of regulatory or legal order; prisoners or participants who are legally institutionalized.

E 25. Participant not suitable for participation, whatever the reason, as judged by the Investigator, including medical or clinical conditions, or participants potentially at risk of noncompliance to study procedures.

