- E 26. Participants are employees of the clinical study site or other individuals directly involved in the conduct of the study, or immediate family members of such individuals (in conjunction with Section 1.61 of the International Council for Harmonisation (ICH)-Good Clinical Practice (GCP) Ordinance E6).
- E 27. Any specific situation during study implementation/course that may rise ethics considerations.
- E 28. Sensitivity to any of the study interventions, or components thereof, or drug or other allergy that, in the opinion of the Investigator, contraindicates participation in the study.

Tumor characteristics for Part-2, Part-3, and Part-4 (new criteria added with amendment 03):

- E 29. Following known genotypes are excluded for expansion cohorts:
 - a) NRAS (except G12A/C)
 - b) RASQ61
 - c) KRASG13
 - d) BRAF Class 1, 2, or unclassified
 - e) PIK3CA

New criteria added with amendment 04

- E 30. Subject has a known activating SHP2 mutation (eg, Noonan syndrome)
- E 31. Treatment with following agents in Part-3 only:
 - KRAS G12C inhibitors (Part-3B only)
 - SHP2 inhibitors (Part-3B only)
 - CYP3A substrates with a narrow therapeutic index

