6.5.1 Prohibited concomitant therapy

In addition to prohibited medications/foods listed in Exclusion Criteria ([Section 5.2](#)), a complete list of prohibited medications during study treatment is provided in Appendix 10 ([Section 10.10](#)).

The following medications are prohibited while on study treatment:

- Medications known to prolong QTc interval
- Anti-cancer therapy (except SAR442720 and pembrolizumab or adagrasib)
- Strong CYP3A4 inhibitors and inducers
- Strong P-gp inhibitors
- Strong BCRP inhibitors (Part-3 only)
- CYP3A substrates with a narrow therapeutic index (Part-3 only)

- Proton pump inhibitors (only during the dose escalation portion of the study; for Part-3 during both escalation and expansion).
- H2-receptor antagonists (only during the dose escalation portion of the study). H2-receptor antagonist can be given at least 2 hours before and 10 hours after adagrasib (Part-3 only).
- Acetylsalicylic acid (low dose aspirin and anticoagulation with low-molecular weight heparin or direct Factor X inhibitors and LMWH are allowed. Prophylactic LMWH is also allowed for high risk patients with hypercoagulability).

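### In Part-3, general permissions for direct Factor X inhibitors and budesonide are not reconciled with the adagrasib-related ban on narrow-index CYP3A substrates

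*Protocol*

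**What the plan says.** **Direct Factor X inhibitors.** Section 6.5 gives a stand-alone permission: "Low dose aspirin and anticoagulation with low-molecular weight heparin or direct Factor X inhibitors and LMWH are allowed". It names no Part. The acetylsalicylic acid bullet of Section 6.5.1 repeats it as a parenthesis: "low dose aspirin and anticoagulation with low-molecular weight heparin or direct Factor X inhibitors and LMWH are allowed". So does the matching bullet of E22 in Section 5.2: "anticoagulation with low-molecular weight heparin or direct Factor X inhibitors and LMWH are allowed". The lead-in to E22 covers adagrasib as well as SAR442720, and the time during treatment as well as before it.

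**The Part-3 ban.** The same list in Section 6.5.1 prohibits "CYP3A substrates with a narrow therapeutic index (Part-3 only" (closing bracket dropped) and sends the reader to Appendix 10 for the drugs concerned. E31 excludes Part-3 candidates treated with "CYP3A substrates with a narrow therapeutic index". Under that class, Appendix 10 names both rivaroxaban and budesonide.

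**Budesonide.** Section 6.6.1.2 (management of diarrhea) and the diarrhea row of Table 11 in Section 2.3.1.1 give octreotide and budesonide as examples of alternatives for refractory cases. Neither place limits this to certain Parts.

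**The concern.** A Part-3 site that needs to start an anticoagulant, or to treat refractory diarrhea, can find text that permits a drug and text that forbids it. Section 2.3.1.5 describes adagrasib as a strong CYP3A inhibitor, which makes narrow-index CYP3A substrates a hazard in this Part. A site that relied on the permissive sentence would give a pairing that the protocol's own list rules out.

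Both situations are foreseeable. Section 2.3.1.1 says that lung cancer participants may be at particular risk of thromboembolism, while noting heavy confounding in those reports. It also records thrombocytopenia with SAR442720 monotherapy in 37 of 113 participants, 17 of them Grade 3-4, though with no accompanying Grade 3-4 bleeding. Diarrhea is among the most frequent toxicities of both drugs. What is at stake is participant safety and consistent practice across sites, not the statistical analysis.

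**Working it through.** No formula applies to the main point, so the check sets the texts side by side.

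| Drug | Permissive text | Prohibitive text | Type of conflict |
|---|---|---|---|
| Rivaroxaban | 6.5, 6.5.1, E22: class of direct Factor X inhibitors allowed, no Part limit | 6.5.1: narrow-index CYP3A substrates barred in Part-3; Appendix 10 names rivaroxaban | Class allowed, one member barred by name |
| Budesonide | 6.6.1.2, Table 11: named for refractory diarrhea, no Part limit | Same 6.5.1 ban; Appendix 10 names budesonide | Allowed by name, barred by name |

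**Does the permission reach Part-3?** Section 6.5 limits it to no Part. In Section 6.5.1 and E22 the authors mark Part-3 limits where they want them, for example on strong BCRP inhibitors, but the anticoagulant wording has no such mark. Section 6.6.1.2 refers to Table 27, whose diarrhea entry covers adagrasib in Part-3, so the diarrhea advice reaches Part-3 too.

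**Does any sentence set the order?** None does. Section 6.5 offers general safeguards, and Appendix 10 advises consulting prescribing information. Its own Medical Monitor instruction concerns drugs that are not listed, whereas both of these are listed. Section 6.6.1.2 does not point to Section 6.5.1 or Appendix 10.

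**Is eligibility affected?** No. Any single exclusion criterion suffices under Section 5.2, so E31 excludes a Part-3 candidate already on either drug. Section 6.3 has the sponsor's Medical Monitor confirm enrollment. The open point is starting either drug during treatment.

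**Scope.** Section 9.2 plans 15 to 30 DLT-evaluable participants in Part-3A and about 40 in Part-3B: 15 + 40 = 55 and 30 + 40 = 70.

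**Background on diarrhea.** Table 11 reports any-grade diarrhea in 55/113 = 48.7% of SAR442720 monotherapy participants, with Grade 3 or higher in 6/113 = 5.3%. Section 2.3.1.4 reports adagrasib-attributed diarrhea in 49.0% of patients. Section 2.3.1.5 anticipates overlapping gastrointestinal toxicity. These are not rates for the combination, and they do not measure budesonide use.

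**The case against.** For rivaroxaban, the two rules can be followed together: a class is allowed and one named member is removed in Part-3. Section 6.5 works this way elsewhere. It allows antiemetics and analgesics in general, while Appendix 10 lists ondansetron, methadone and fentanyl. The amendment history points the same way: amendment 03 added Factor X inhibitors to Section 6.5, and amendment 04 later added the adagrasib prohibitions to Section 6.5.1. Where a Part-3 exception was wanted, as for H2-receptor antagonists, it was written into the list. In E22 and Section 6.5.1 the permission is also only a parenthesis to the aspirin bullet.

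There are further safeguards. Section 6.5 requires participants to abstain from drugs "unless, in the opinion of the Investigator and Sponsor, the medication will not interfere with the study", and adds: "The Medical Monitor should be contacted if there are any questions regarding concomitant or prior therapy". Appendix 10 calls for a check of the prescribing information for any concomitant drug. Section 6.6.1.1 interrupts adagrasib for signs of thrombosis and stops it permanently for clinically significant thromboembolic complications. If that applies to every Part-3 participant, it largely closes off the case of a new clot treated with rivaroxaban while adagrasib continues. Its heading may limit it to users of hormonal contraceptives.

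Most of this stands for rivaroxaban and lowers the risk. It does not remove the ambiguity, because a site that reads an explicit permission may see no question to ask. The class-and-member argument fails for budesonide, which is named on both sides. It remains true that budesonide is only an optional example, that octreotide is named beside it, and that a careful reader would give way to the Part-3 ban.

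**Conclusion.** The point holds as a minor safety clarification. For rivaroxaban the Part-3 ban is the natural rule, but it is left to inference. For budesonide the conflict is direct and concerns a toxicity expected with both drugs. The text governs about 55 to 70 planned participants. The documents give neither a rate of use for either drug nor the size of either interaction, so no count of affected participants and no degree of harm can be stated. No endpoint, sample size or analysis changes.

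This rests on reading the Appendix 10 class as operative in Part-3 through Section 6.5.1, and on the planned enrollment.

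Three stronger readings are not supported. A reader might infer that Part-3 could enroll people already on these drugs; E31 prevents that. A reader might infer that barring rivaroxaban forces a site to use low-molecular-weight heparin. The text does not say so: the permission still covers other direct Factor X inhibitors, subject to Appendix 10's note that its list is not comprehensive. A reader might also infer that the protocol gives no guidance on which rule to follow. It gives several pointers, but no stated order.

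**What to change.** In Section 6.5, and in the matching parentheses of Section 6.5.1 and E22, add: *except, in Part-3, rivaroxaban and any other narrow-therapeutic-index CYP3A substrate (Appendix 10)*. In Section 6.6.1.2 and the diarrhea row of Table 11, add: *not budesonide in Part-3*.

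The cost is a few words in five places in one amendment. No procedure, visit or participant is added. Low-molecular-weight heparin for anticoagulation and octreotide for refractory diarrhea remain available under the existing text.

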6.5.1 Prohibited concomitant therapy

In addition to prohibited medications/foods listed in Exclusion Criteria ([Section 5.2](#)), a complete list of prohibited medications during study treatment is provided in Appendix 10 ([Section 10.10](#)).

The following medications are prohibited while on study treatment:

- Medications known to prolong QTc interval
- Anti-cancer therapy (except SAR442720 and pembrolizumab or adagrasib)
- Strong CYP3A4 inhibitors and inducers
- Strong P-gp inhibitors
- Strong BCRP inhibitors (Part-3 only)
- CYP3A substrates with a narrow therapeutic index (Part-3 only)

- Proton pump inhibitors (only during the dose escalation portion of the study; for Part-3 during both escalation and expansion).
- H2-receptor antagonists (only during the dose escalation portion of the study). H2-receptor antagonist can be given at least 2 hours before and 10 hours after adagrasib (Part-3 only).
- Acetylsalicylic acid (low dose aspirin and anticoagulation with low-molecular weight heparin or direct Factor X inhibitors and LMWH are allowed. Prophylactic LMWH is also allowed for high risk patients with hypercoagulability).

6.6 DOSE MODIFICATION

A 21-day cycle will be maintained, and dose interruption will be noted in the 21-day cycle schedule.

In the Dose Escalation cohorts, there will be no dose reductions or modifications during C1, 21-day DLT assessment period unless a DLT has occurred. After Cycle 1 and in the final dose cohort, if a dose reduction is recommended, then the SAR442720 dose level should be the previous lower dose level considered to be tolerable in prior participants receiving that dose. Two dose reductions are allowed.

In Part-2, dose reduction will be allowed for SAR442720 according to the criteria detailed below. SAR442720 may be reduced to the dose corresponding to one dose level below RP2D. Pembrolizumab dose reductions are not permitted. Pembrolizumab treatment may be interrupted or discontinued due to toxicity.

In Part-3, dose reduction for SAR442720 will be as described below. SAR442720 may be reduced to the dose corresponding to one dose level below.

In Part-4, dose reduction of SAR442720 is not allowed on C1D1, C1D15, and C2D1. For other doses, dose reduction or interruption may be allowed. Pembrolizumab dose reductions are not permitted. Pembrolizumab treatment may be interrupted or discontinued due to toxicity.

Two types of dose modifications are allowed, “dose interruption” and “dose level reduction” according to the dose modification criteria and guidelines outlined in [Section 6.6.1](#) below. Any allowed dose modification and any deviation from the intended dose (missed doses or overdoses due to participant error) should be documented on the dose eCRF.

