The Study Committee will review clinical data on a regular basis, with a review being performed at least at the end of each DL cohort, before the enrollment of new participants at the next DL, and at the end of the dose escalation phase of the study. The Study Committee in agreement with the Sponsor's Study Medical Manager will decide on whether to escalate or de-escalate to the next DL or to add alternative dose levels during Study Committee meetings based on current safety profile and tolerability, available PK information, and statistical design recommendation. Decisions regarding participant treatment and cohort expansion will be discussed and clearly documented in the discussion minutes. The Study Committee in agreement with the Sponsor's Study Medical Manager may permit the evaluation of additional DLs and/or additional schedules of administration of SAR442720 and adagrasib, depending upon the observed safety and DLT at each DL, and the safety and/or PK data observed in the ongoing study.

In Part-3A approximately 15 to 30 DLT evaluable participants are expected to be enrolled during the Dose Escalation. The design of the study assumes 5 combination dose levels with 3 to 6 participants per dose level.

Part-3B

The Part-3B dose expansion will assess the anti-tumor activity and safety of SAR442720 combined with adagrasib in participants with NSCLC harboring KRAS G12C mutation.

The Part-3B dose expansion of the study will start once RP2D for SAR442720 and adagrasib from the Part-3A dose escalation is confirmed.

Approximately 40 participants will be enrolled in Part-3B dose expansion and treated at the RP2D identified in Part-3A (see [Section 9.2](#)).

“Note: Enrolled participants are all participants from screened participants who have been allocated to an intervention regardless of whether the intervention was received or not”.

Part-4

The Part-4 of this Phase 1/2, open-label, multi-center, non-randomized study will assess the effect of food on the PK of SAR442720 tablet, when dosed in combination with pembrolizumab in participants with advanced malignancies. It will also evaluate the relative bioavailability of SAR442720 tablet formulation (test) compared to the SAR442720 capsule formulation (reference) when dosed in combination with pembrolizumab in participants with advanced malignancies.

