4.1.2 Dose escalation

In Part-1 and Part-3A, dose escalation will follow mTPI2 design with a minimum of 3 participants evaluable for DLT in the first cycle. A participant will be considered evaluable for DLT assessment if he/she receives at least 4 out of the 6 planned doses of SAR442720 in the first cycle and completes the DLT observation period or if he/she experiences a DLT in the DLT observation period. A participant who is not DLT-evaluable will be replaced to achieve a minimum of 3 DLT-evaluable participants at the same cohort.

The actual dose selected at each dose escalation decision, and the MTD identified at the conclusion of the dose escalation phase, will be determined by the Study Committee, in agreement with the Sponsor's Study Medical Manager, which may select a dose at or below the model's recommendation and should not select a dose that is suggested to be over toxic by the model. The Study Committee will review the overall safety of all dose levels. More details in the model and its operating characteristics can be found in Appendix 11 ([Section 10.11](#)).

The adaptive dose escalation design is based on the boundaries generated from the mTPI2 design. The dose escalation will stop if the next recommended dose has been collectively evaluated in at least 2 previous escalation cohorts.

It is anticipated that in Part-1 12 to 18 DLT-evaluable participants and in Part-3A 15 to 30 DLT-evaluable participants will be enrolled in the dose escalation. The actual total number of participants required will depend on the number of dose levels evaluated and on the incidence and timing of observed DLTs.

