6.6.1 Dose modification criteria

6.6.1.1 General guidelines for adagrasib (Part-3)

The following are the general guidelines for withholding, resumption or re-challenge of treatment with adagrasib:

- following adagrasib dose reduction and control of an AE, re-challenge at a higher adagrasib dose may be permitted after discussion with the Sponsor;

- if resumption of dosing for adagrasib is delayed for ≥ 14 days due to an AE that is at least suspected to be attributable to study treatment, then resumption at a reduced dose should be considered;
- if treatment with adagrasib is withheld for ≥ 22 consecutive days, then permanent discontinuation from treatment with one or both agents should be considered; and
- if a treatment-related AE recurs despite dose reduction of adagrasib to the lowest dose anticipated, then permanent discontinuation from study treatment should be considered, unless after discussion with the Sponsor it is considered to be in the best interest of the participant to continue.

Treatment interruptions and modification guidelines are provided in Appendix 9 ([Section 10.9](#)).

Additional guidelines for adagrasib:

Hepatic Toxicities

Hepatic toxicities that are considered to be causally related to adagrasib should initially be managed with treatment interruption of one or both study drugs as outlined in [Table 27](#). Evaluations for confounding factors (eg, cholestasis, metastasis, or viral infection) should be performed as clinically indicated, and more frequent monitoring of a hepatic panel (including AST, ALT, alkaline phosphatase, and bilirubin) should be considered for those participants with transaminase increases. Following resolution of toxicity to the specified degree, dose reduction of adagrasib should be implemented.

Other Laboratory Investigation-Based Toxicities

Other laboratory investigation-based toxicities that are considered to be causally related to adagrasib should initially be managed with treatment interruption of adagrasib as outlined in [Table 27](#). Following resolution of toxicity to the specified degree, dose reduction of adagrasib should be implemented.

Cardiac Toxicities

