Cardiac toxicities that are considered to be causally related to adagrasib should initially be managed with treatment interruption of adagrasib as outlined in [Table 27](#). Cardiology consultation should be obtained for cases of QTcF prolongation or LVEF decreases falling into the categories indicated in [Table 27](#). In addition, more frequent monitoring of electrolytes that include potassium and magnesium should be considered for participants with vomiting, diarrhea, or past instances of hypokalemia or hypomagnesemia that could recur, and oral and/or intravenous supplementation should be considered for levels below the lower limit of normal. Additionally, arrhythmia should be included in the differential diagnosis of relevant AEs (eg, palpitations, syncope, pre-syncope, or unexplained dyspnea), and unscheduled ECGs should be performed for participants with such events or electrolyte abnormalities as clinically indicated. Additional assessments of LVEF should be performed as clinically indicated at the Investigator's discretion if there are signs or symptoms of cardiotoxicity.

Following resolution of toxicity to the specified degree, dose reduction of adagrasib should be implemented.

Pneumonitis

Pneumonitis has been reported in the Phase 1 study of adagrasib. An evaluation should be performed to assess the attribution of pneumonitis to adagrasib. Pneumonitis considered to be causally related to adagrasib should be initially managed with treatment interruption of adagrasib as outlined in [Table 27](#). Following resolution of toxicity to the specified degree, dose reduction of adagrasib should be implemented.

Other Toxicities

Other toxicities that are considered to be causally related to adagrasib should initially be managed with treatment interruption as outlined in [Table 27](#). Following resolution of toxicity to the specified degree, dose reduction of adagrasib should be implemented.

Hormonal Contraceptives and Thrombotic Events

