7.1.2 Temporary discontinuation

Temporary intervention discontinuation may be considered by the Investigator because of suspected AEs as described in [Section 6.6](#) or disruption of the clinical trial due to a regional or national emergency declared by a governmental agency (eg, COVID-19) ([Section 10.12](#)). For all temporary intervention discontinuations, duration should be recorded by the Investigator in the appropriate pages of the CRF or eCRF.

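### Part-3A: the Cycle 1 bar on dose modification conflicts with the directed safety holds, and DLT-evaluability is defined three ways

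*Protocol*

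**What the plan says.** **Cycle 1 modification.** Protocol Section 6.6: "In the Dose Escalation cohorts, there will be no dose reductions or modifications during C1, 21-day DLT assessment period unless a DLT has occurred". The same section says "Two types of dose modifications are allowed" and names them as interruption and dose-level reduction, so on a literal reading the bar covers holds as well. Part-3A falls under it. Section 4.1.2 says "In Part-1 and Part-3A, dose escalation will follow mTPI2 design", and Section 4.1 says "In Part-3A approximately 15 to 30 DLT evaluable participants are expected to be enrolled during the Dose Escalation". The Part-3 paragraph of 6.6 ("In Part-3, dose reduction for SAR442720 will be as described below") does not lift the bar.

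**Directed holds and reductions.** Section 6.6.1.1 says of hepatic toxicity, after interruption, "Following resolution of toxicity to the specified degree, dose reduction of adagrasib should be implemented", and of pneumonitis, "Pneumonitis considered to be causally related to adagrasib should be initially managed with treatment interruption of adagrasib". Tables 11 and 27 direct interruption for Grade 3-4 thrombocytopenia without bleeding; Table 27 applies this to both drugs. For Part-3, Table 27 also directs a one-level adagrasib reduction for Grade 2 AST/ALT, and an adagrasib hold for Grade 2 pneumonitis with a lower dose if resumed. None of these entries has a Cycle 1 exception.

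**DLT criteria (Section 4.1.1).** Grade 3 thrombocytopenia is a DLT only with clinically significant bleeding. Isolated Grade 2 liver tests and Grade 2 pneumonitis are not listed. Related toxicity that leaves SAR442720 dose intensity at 50% or less is a DLT, in a sentence that ends with a condition about absence of recovery. Toxicity that leaves less than 66.7% of adagrasib delivered is a DLT.

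**DLT-evaluable, Part-3A.**
- Synopsis and Section 4.1: 80% of both drugs in 21 days, with no clause for a participant who has a DLT.
- Section 4.1.2: 4/6 SAR442720 doses with no adagrasib minimum, or a DLT.
- Section 9.3 Table 20 and SAP Table 3: 4/6 and 28/42 adagrasib doses, or a DLT.

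**The concern.** Incidence of Cycle 1 DLTs is a primary endpoint of Part-3A, and Section 9.4.1 rests the MTD recommendation on Cycle 1 data in the DLT-evaluable set. Two sets of instructions that feed this endpoint contradict each other.

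(A) For a toxicity that is not a DLT, Section 6.6 tells the site to leave dosing alone in Cycle 1, and Table 27 tells it to hold or reduce. The dose-intensity DLT criteria and the evaluability minimums presuppose that Cycle 1 holds occur. If no hold is allowed before a DLT, a compliant hold could never produce a dose-intensity DLT.

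(B) A participant with a short hold can be kept under one definition of evaluable and replaced under another. Read literally, the 80% rule would also remove a participant who stopped early because of a DLT.

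Cohorts are small. One participant is 1/3 = 33 points of observed DLT rate in a cohort of 3, and 1/6 = 17 points in a cohort of 6.

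**Working it through.** **Planned doses.** SAR442720 on Days 1, 2, 8, 9, 15 and 16 gives 6. Adagrasib twice daily for 21 days gives 2 × 21 = 42. These match Table 20. Its minimums are 4/6 = 28/42 = 66.67%. The 80% rule needs 0.8 × 6 = 4.8, so 5/6, and 0.8 × 42 = 33.6, so 34/42.

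**Both drugs held for L whole days.** Adagrasib doses left = 42 − 2L.

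| L (days) | Adagrasib left | Table 20 (28/42) | 80% rule (34/42) | 66.7% DLT limit |
|---|---|---|---|---|
| 4 | 34 (81.0%) | met | met | not a DLT |
| 5 | 32 (76.2%) | met | failed | not a DLT |
| 6 | 30 (71.4%) | met | failed | not a DLT |
| 7 | 28 (66.67%) | met | failed | on the limit |
| 8 | 26 (61.9%) | failed | failed | DLT |

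**All single both-drug holds inside Cycle 1 that start on Day 2 or later.** There are 21 − L holds of length L.
- Total: 20 + 19 + … + 1 = 210.
- L of 8 or more: 13 + 12 + … + 1 = 91, all DLTs on the adagrasib criterion.
- L of 7 or less: 210 − 91 = 119, all with at least 4/6 and 28/42.
- Of these 119, failing the 80% rule: all with L = 5 to 7 (16 + 15 + 14 = 45), plus those with L = 2 to 4 that cover two SAR442720 doses (2 + 4 + 6 = 12; for example Days 8-9). Total 57.
- All 14 seven-day holds leave exactly 4/6 and 28/42. This is two-thirds, and just under 66.7% if that figure is read to more decimals.

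**One event, three results: related Grade 3 thrombocytopenia without bleeding.**
- Dosed through as 6.6 reads: 6/6 and 42/42; evaluable, no DLT.
- Held Days 15-21: 4/6 and 28/42; evaluable under Table 20 and no DLT if 28/42 meets the limit, but replaced under the 80% rule.
- Held Days 14-21: 4/6 and 26/42; a DLT.

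**Missing DLT clause.** A participant who stops both drugs after Day 7 because of a DLT has 2/6 and 14/42 (33.3%). Table 20 keeps this participant; the 80% sentence, taken alone, does not.

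**SAR442720 criterion.** A SAR442720-only hold over Days 8-15 leaves 3/6 and 42/42. If the recovery condition in 4.1.1 applies to this criterion and the participant has recovered, this is not a DLT on that criterion. At 3/6 it is not evaluable either.

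**Reach, thrombocytopenia only.** Table 11 gives Grade 3-4 events in 17/113 = 15.0% on monotherapy. Times 15 to 30 participants, that is 2.3 to 4.5. The any-grade median onset is 15 days. If half of the Grade 3-4 events start by then (assumption), 1.1 to 2.3 participants are affected. With 25% to 75% starting by then, the range is 0.25 × 2.26 = 0.6 to 0.75 × 4.51 = 3.4.

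**Effect on status.** The Part-3 schedule (Table 4) has Cycle 1 laboratory tests on Days 1, 8 and 15, the last two ±1 day. A hold that starts on Day 15 or later loses at most 7 days, so it leaves at least 4/6 and 28/42. A change of DLT status therefore generally needs detection around Day 8, on Day 14 at the edge of the window, or at an unscheduled test.

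**Effect on a decision.** The mTPI2 target is redacted. Under assumed targets of 0.20 to 0.30 with interval half-widths of 0.03 to 0.05, 0/3 gives escalate and 1/3 gives stay or de-escalate.

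**The case against.** The strongest reply to (B) is that Section 9.2 sends the reader to Section 9.3 for the definition of DLT-evaluable, SAP Table 3 agrees with it, and the MTD rests on that population. This stands. A reader might infer that the analysis set is undefined; the documents do not support that. What remains is that a site or the Study Committee following the synopsis or 4.1 would replace participants whom the analysis keeps.

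On (A), Appendix 9 calls Tables 26 and 27 guidelines, another Table 27 row makes the thrombocytopenia hold conditional on clinical need, 6.6 opens by saying that interruptions are noted within the 21-day cycle, and Section 7.1.2 says "Temporary intervention discontinuation may be considered by the Investigator because of suspected AEs as described in" Section 6.6. So the reading that sites must dose through toxicity goes too far. But 7.1.2 leads back to the section that contains the bar, and no text sets precedence.

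Dosing through and holding for 8 days do differ in dose intensity, and the criterion is meant to register that. True. The defect is that the protocol gives opposite directions on which course to take.

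Two other strong readings fail. One is that a hold through Day 16 must be a DLT on the SAR442720 criterion: the recovery condition leaves this open. The other is that one evaluability definition makes every participant either a DLT or evaluable: the enumeration covers both-drug holds only, and the 3/6 with 42/42 case can be neither.

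Several facts make the reach estimate lean high. Treatment-related Grade 3 or higher thrombocytopenia was 13.3%. The 15.0% pools all monotherapy dosing cohorts, and the intermittent schedule may be better tolerated. The SAR442720 starting dose was halved for the expected interaction. Table 14 lists no adagrasib level below 400 mg BID, so a listed Grade 2 liver-test reduction exists only at DL3a and DL4. Review of each potential DLT by the Sponsor and recruiting Investigators also limits the effect, but it does not choose an evaluability definition.

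**Conclusion.** Both contradictions are in the current text and neither document resolves them. (A) is a conflict of instructions in Cycle 1, softened by the guideline status of Appendix 9 and by 7.1.2. (B) leaves the analysis set largely settled by Table 20, but the 80% rule would wrongly drive replacement (57 of the 119 both-drug holds of 7 days or less) and, literally, would exclude a participant who stopped early for a DLT.

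The reach is small: roughly 1 to 2 of 15 to 30 participants would face the Cycle 1 conflict through thrombocytopenia (0.6 to 3.4 over the assumed onset split), and fewer would change DLT status. This rests on monotherapy rates and on Grade 3-4 events starting when any-grade events do. It includes Grade 4 events, which are DLTs already. It omits Grade 2 AST/ALT and Grade 2 pneumonitis, for which no rates are given, and it does not model the possible 2-fold rise in SAR442720 exposure with adagrasib. It is an order of magnitude, not a bound. Because a single classification can turn escalate into stay or de-escalate in a cohort of 3, the wording should be fixed.

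**What to change.** 1. Amend Section 6.6 to permit safety interruptions under 6.6.1 and Appendix 9 in Cycle 1 for toxicity that is not a DLT, counted through the existing dose-intensity DLT criteria. State whether the Table 27 reductions for non-DLT events apply in Cycle 1.
2. Delete the 80% rule from the synopsis and Section 4.1. Use the Table 20 definition throughout, including its DLT clause, and add 28/42 to Section 4.1.2. State that 28/42 meets the 66.7% limit.
3. State in Section 4.1.1 whether the recovery condition applies to the SAR442720 dose-intensity criterion. If it does, say how a recovered participant with 3/6 or fewer SAR442720 doses is handled.

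The cost is protocol wording plus one SAP sentence on the 66.7% limit; SAP Table 3 already uses 4/6 and 28/42. No participants are added, and dropping the 80% rule keeps some who would otherwise be replaced.
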